Milestones	
 
 Registration in the EU PAS register	May 2021	
 
 Start of data permit process	March 2021	
 
 End of data permit process	December 2021	
 
 Start of data extraction (for Denmark)	August 2021	
 
 End of data extraction (for Denmark)	September 2021	
 
 Start of data extraction (for Sweden)	January 2022	
 
 End of data extraction (for Sweden)	February 2022	
 
	Registration in the EU PAS register	May 2021	Start of data permit process	March 2021	End of data permit process	December 2021	Start of data extraction (for Denmark)	August 2021	End of data extraction (for Denmark)	September 2021	Start of data extraction (for Sweden)	January 2022	End of data extraction (for Sweden)	February 2022
Registration in the EU PAS register	May 2021														
Start of data permit process	March 2021														
End of data permit process	December 2021														
Start of data extraction (for Denmark)	August 2021														
End of data extraction (for Denmark)	September 2021														
Start of data extraction (for Sweden)	January 2022														
End of data extraction (for Sweden)	February 2022														

	Start of interim data analysis	September 2021
	End of interim data analysis	December 2021
	Start of interim study reporting process	January 2022
	Interim report of study results	April 2022
	Start of final data analysis	March 2022
	End of final data analysis	June 2022
	Start of final study reporting process	June 2022
	Final report of study results	July 2022
	Start of manuscript writing process	September 2022
	Final manuscript delivery	November 2022

5 Amendments and Updates

None.

6 Milestones

The following table estimates timelines for the milestones of this multi-country study, combining results from each country.

Milestone	Planned date
Registration in the EU PAS register	May 2021
Start of data permit process	March 2021
End of data permit process	December 2021
Start of data extraction (for Denmark)	August 2021
End of data extraction (for Denmark)	September 2021
Start of data extraction (for Sweden)	January 2022
End of data extraction (for Sweden)	February 2022
Start of interim data analysis ⁺	September 2021
End of interim data analysis ⁺	December 2021

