The overall study period will be between 2010 and 2020. Different study period starts will be applied depending on which two drugs are being compared. For the comparison between rhFSH-alfa reference product and HP-hMG, the study period will start 1 January 2010 for both countries. This date is selected to ensure the study is sufficiently powered while also reducing heterogeneity in patient management over time. Changes that have occurred over time include moving towards vitrification rather than slow freezing for embryo cryopreservation and hence also moving from cleavage stage to blastocyst embryo transfers, elective single embryo transfers rather than double embryo transfers, and antagonist protocols rather than agonist protocols. For the comparison between rhFSH-alfa reference product and rhFSH-alfa biosimilar products, the study period will start 26 March 2014 for Denmark and 20 June 2014 for Sweden. These are the earliest dates when a rhFSH-alfa biosimilar product (Bemfola) received reimbursement status in each country. For

Sweden, where the IVF register is updated annually and has a lag time of approximately two years (see Section 9.4.2), inclusion of women undergoing IVF/ICSI treatment may end on 31 December 2019, depending on data availability at the time of data extraction. No such general restriction will be applied for Denmark, as the IVF register is updated monthly. In terms of follow-up of IVF/ICSI treatment and pregnancy outcomes, the study will end on 31 December 2020 (or last available date) for each country. Specifically, for the main analyses of the primary objective (LBR, CLBR and MC-CLBR) and secondary objective 4 (TTLB), a minimum follow-up period of 1 year has been chosen to allow sufficient time to achieve (at least) one live birth and a reasonable number of complete cycles for reliable estimates of live birth rates. Hence, the corresponding analyses are restricted to cycles initiated on or before 31 December 2019 (Sets 1 and 5 in Table 5). The minimum follow-up period will be extended to 2 years in a sensitivity analysis to explore the potential effect this has on the estimated MC-CLBR and TTLB (see sensitivity analysis 3 in Table 8).

To reduce possible bias linked to confounding by baseline characteristics, inverse probability of treatment weighting (IPTW), based on propensity scores (PS) (22), will be used to balance the distribution of potential confounders across the study cohorts.

Figure 1. Study design

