The Danish Medical Birth Register (DMBR) is an enrichment of data already recorded in the DNPR and compiles relevant information of pregnancies that has led to childbirth in Denmark at home or in a hospital (30). It contains information on characteristics of mother and child, pregnancy and delivery characteristics including induction procedures and gestational age, outcomes of pregnancy and delivery, and the mother's history of previous abortions and/or deliveries. The DMBR includes linkage between infant, mother and father. The DMBR has been in operation since 1973, with later improvements, particularly in 1997. The register is updated once a year after end of December with a lag of 13 months, partly due to the enrichment on information on date of death within the first year after birth.

The Danish Register of Medicinal Product Statistics (RMPS) contains patient-level data on all prescription drugs filled by patients at community pharmacies (31,32), but not medication administered at hospitals. The administrative purpose of the register is to administer how the cost is split between the health care system, the municipality and the patient's co-payment. Thus, completeness and accuracy of data collection is very high. The register contains information on the date of purchase, item number, product name, ATC code, strength per unit, quantity of DDDs (as per the World Health Organization (WHO)) per package and number of packages filled. Data is available from 1995 and onwards. Since April 2004, information on medical indication for prescription and daily prescribed dose by physician has also been available, but completeness and validity are affected by a non-compulsory obligation to record this information.

The Danish Register of Laboratory Results for Research (RLRR) is managed by the Danish Health Data Authority. It has information on laboratory tests at the country's major clinical biochemical and clinical immunological laboratories. Laboratory results are first collected in the National Lab Databank. General practitioners, specialists in private practices and private fertility clinics can forward samples for analysis to the hospital laboratories, when they do not have the capacity/equipment to do the analysis themselves, and these tests are also included in the National Lab Databank. All this information is transferred to the RLRR later. If a patient, proactively, has denied consent to exchange lab results, the results are not transferred to the RLRR.

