9.7.1 Analysis Sets

To address the study objectives, analysis sets will be constructed based on the study outcomes as defined in Section 9.1.2. To allow for a sufficient time period to assess the outcomes after the initiation of a stimulation cycle, the analysis sets will be restricted to outcome-specific time periods. For the analysis sets, the following outcome-specific time periods are applied: 1 year after the stimulation cycle initiation for LBR, CPR, OPR, MC-CLBR and TTLB; 1 year after the stimulation cycle and linked FET initiation for CLBR, CCPR, COPR, pregnancy loss, multiple pregnancy and treatment-associated costs; 1.5 months after the stimulation cycle initiation for oocyte retrieval and embryos cryopreserved per initiated stimulation cycle, and cycle cancellation; 1 month after the stimulation cycle aspiration for oocyte retrieval and embryos cryopreserved per aspirated stimulation cycle; 4 months after stimulation cycle initiation for OHSS; 3 months after last embryo transfer for implantation. Fresh and frozen embryo transfers will be assessed by using all fresh and frozen embryo transfers done by the end of the study period (31 December 2020).

The analysis sets and their use for the study objectives and outcomes are defined in Table 5. The use of analysis sets will be described in the statistical analysis, and any needed specific modifications or restrictions on the analysis sets needed for the analysis of the study objectives will be further described in the SAP.

Table 5. Description of analysis sets

Analysis set	Description of the analysis set	Study objective(s)	Study outcome measure(s)
Set 1	Stimulation cycles with drug of interest initiated on or before 31 December 2019	Primary objective	LBR
		Secondary objective 1	CPR
			OPR
Set 2	Stimulation cycles with drug of interest and linked FET cycles initiated on or before 31 December 2019	Primary objective	CLBR
		Secondary objective 1	CCPR
			COPR
		Secondary objective 5	Pregnancy loss
		Secondary objective 6	Multiple pregnancy
Secondary objective 9	Treatment-associated costs		
Set 3	Stimulation cycles with drug of interest initiated on or before 15 November 2020 ⁺	Secondary objective 2	Oocytes retrieved per initiated stimulation cycle
			Embryos cryopreserved per initiated stimulation cycle
			Utilizable embryos per initiated stimulation cycle
		Secondary objective 7	Cycle cancellation

Analysis set	Description of the analysis set	Study objective(s)	Study outcome measure(s)

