9.7.2 Derived and Transformed Data

The data sources included for this study are national healthcare registers that are expected to have a comprehensive coverage and high-quality data. Thus, large amounts of missing data is not expected to be an issue in this study. In case of missing data, a missing data category will be added, and the number of observations and patients with missing data will be reported for each measured variable in the study. The handling of missing data will be described in more detail in the SAP.

The IVF registries may record some of study covariates related to patient characteristics (see Table 1, section 9.3.2), such as smoking status or BMI, only for the patient's first stimulation cycle. Thus, the covariate value from the patient's first stimulation cycle will be used also for the patient's subsequent cycles if the covariate values for the subsequent cycles are missing.

Any study variables and outcomes that are only recorded if an event occurs, such as live birth, are not considered missing. Also, any outcomes relying on the presence of a diagnostic code (i.e. ICD-10), such as OHSS, fit this definition.

Any derived and transformed data needed for conducting the statistical analysis will be described in the SAP.

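### Danish live births in 2020 are not due in the birth register until about January 2022, after the planned extraction, yet cycles started up to 31 December 2019 stay in the live-birth analyses

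*Protocol*

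**What the plan says.** **Source of live birth.** Sections 9.1.2.1 and 14.3.1 take Danish live births from the DMBR alone; Sweden has both its birth register and its IVF register. Section 9.4.1 states that the Danish IVF register holds no pregnancy outcome, so it cannot stand in.

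**Lag.** Section 9.4.1 says of the DMBR: "The register is updated once a year after end of December with a lag of 13 months". Part of the reason given is that deaths in the first year after birth are added.

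**Extraction.** Section 6 lists "End of data extraction (for Denmark) September 2021", with a start in August 2021.

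**Cut-off.** For the live-birth outcomes, section 9.1.1 says that "a minimum follow-up period of 1 year has been chosen to allow sufficient time to achieve (at least) one live birth" and that "the corresponding analyses are restricted to cycles initiated on or before 31 December 2019". Table 5 defines Set 1 as "Stimulation cycles with drug of interest initiated on or before 31 December 2019"; Sets 2 and 8 carry the same date.

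**Danish restriction.** After describing the Swedish IVF register lag, section 9.1.1 adds: "No such general restriction will be applied for Denmark, as the IVF register is updated monthly".

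**No record.** Section 9.7.2 says: "Any study variables and outcomes that are only recorded if an event occurs, such as live birth, are not considered missing".

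**The concern.** The cut-off of 31 December 2019 was chosen so that the last cycle has a year in which a birth can be observed. That year exists only if the extracted birth data run to the end of 2020. The protocol checks this for Denmark against the IVF register, which is updated monthly, and not against the birth register, which sets the real limit.

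If births are complete only to the end of 2019, most cycles from the last nine months of inclusion enter the denominator with no chance, or a reduced chance, of entering the numerator. This lowers the Danish LBR, CLBR and MC-CLBR. If the affected cycles are spread unevenly between products, it also produces a difference that has nothing to do with the drugs.

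**Working it through.** **1. The plan's own figure.** From 31 December 2019 to 31 December 2020 is 366 days. The stated minimum of 1 year reproduces if birth data run to the end of 2020.

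**2. When the births become available.** Availability = end of calendar year + 13 months.
- 2019 births: 31 December 2019 + 13 months = about 31 January 2021.
- 2020 births: 31 December 2020 + 13 months = about 31 January 2022, which is 4 to 6 months after the August-September 2021 extraction.

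At the planned extraction, births are complete to 31 December 2019. Observable follow-up for a cycle started that day is 0 days, not 366.

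**3. Which cycles are affected.** Assumption: stimulation start is close to the last menstrual period. Last start with an observable birth = 31 December 2019 minus gestation.

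| Gestation at birth | Birth missed if cycle started after | Window |
|---|---|---|
| 40 weeks (280 days) | 26 March 2019 | 9.2 months |
| 37 weeks (259 days) | 16 April 2019 | 8.5 months |
| 22 weeks (154 days; lower limit in section 9.1.2.1) | 30 July 2019 | 5.1 months |

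**4. Share of Danish cycles, assuming even volume.** The HP-hMG comparison runs for 120 months (2010-2019). The biosimilar comparison runs for 69.2 months (26 March 2014 to 31 December 2019).
- HP-hMG comparison: 9.2/120 = 7.7%. On Table 2 volumes this is about 4,060 of 53,000 reference cycles and 2,530 of 33,000 HP-hMG cycles. Wholly blind part: 5.1/120 = 4.3%.
- Biosimilar comparison: 9.2/69.2 = 13.3%, or about 4,120 of 31,000 reference cycles and 660 of 5,000 biosimilar cycles. Wholly blind part: 5.1/69.2 = 7.4%.

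These shares fit fresh-transfer LBR. For CLBR and MC-CLBR the loss reaches further back, because a frozen transfer or later stimulation cycle started in 2019 can lose its birth even when the first cycle was earlier.

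**5. Is the loss differential?** Section 9.9.2 says biosimilar use grew gradually and was relatively larger late in the period. Table 1 lists calendar year as a baseline characteristic, but not as a propensity-score candidate or for additional adjustment. The planned weighting therefore does not balance it directly.

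**6. Illustration only.** The protocol gives no yearly shares by product. Assume the same true LBR p in both cohorts, 13% of reference cycles in the window, and every cycle in the window scored as a failure. Observed LBR = p × (1 − share).

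| p | Biosimilar share in window | Reference | Biosimilar | Gap (points) | OR |
|---|---|---|---|---|---|
| 25% | 13% | 21.75% | 21.75% | 0 | 1.00 |
| 25% | 20% | 21.75% | 20.00% | 1.75 | 1.11 |
| 25% | 25% | 21.75% | 18.75% | 3.0 | 1.20 |
| 20% | 20% to 25% | 17.4% | 16.0% to 15.0% | 1.4 to 2.4 | 1.11 to 1.19 |
| 30% | 20% to 25% | 26.1% | 24.0% to 22.5% | 2.1 to 3.6 | 1.12 to 1.22 |

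The last assumption overstates the loss somewhat, since some earlier births would be recorded.

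**7. Contrast with Sweden.** Section 9.4.2 says a year's births are usually available the following December. Births in 2020 are then due in December 2021, before the Swedish extraction in January-February 2022. The problem is Danish only.

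**The case against.** **The date may move.** The footnote in section 6 and section 9.7.4 say Danish data access has been delayed and may end up on a timetable like Sweden's. Extraction in January-February 2022 would find the 2020 births at or near availability. This stands, and makes the point conditional on the stated milestones. But those milestones were not revised, and nothing makes extraction wait for the DMBR release.

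**The plan leaves room to adjust.** Follow-up may end at the last available date, and section 9.7.1 leaves further modifications of the analysis sets to the SAP. That gives a route to a repair, but the first moves only the end of follow-up and the second states no rule. The one adjustment rule in Table 5 is triggered by the Swedish IVF register and is not marked on Sets 1, 2 or 8.

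**The not-missing sentence is about data coding, not register lag.** This is fair, but Table 7 leads to the same place: LBR and CLBR are divided by all initiated cycles, so an unrecorded birth lowers the rate.

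**Mitigation exists.** Sensitivity analysis 3 restricts MC-CLBR and TTLB to first-ever cycles by 31 December 2018. It does not cover LBR or CLBR. With births to the end of 2019, its promised 2 years become 1, and births from cycles or frozen transfers started during 2019 are still lost. TTLB also censors at end of study, but its time unit is cycle rank, so censoring may not fully protect it. Section 9.9.2 concedes a possible downward bias for biosimilars, but only for cumulative outcomes and from shorter follow-up.

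**Conclusion.** The point holds on the stated milestones. The Danish birth data will stop a year short of what the cut-off for Sets 1, 2 and 8 assumes, and Danish live-birth rates will be too low. With even volume, the window holds about 7.7% of cycles in the HP-hMG comparison and 13% in the biosimilar comparison. In the latter, the bias probably favours the reference product. Its size is not known from the document; 1.75 to 3.0 points (OR 1.11 to 1.20, at an assumed LBR of 25%) is an illustration.

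A reader might infer more than the protocol supports:
- *That every birth from cycles started after late March 2019 is lost.* Births before term are recovered in part; only cycles started after about 30 July 2019 are wholly blind.
- *That the loss is certain.* It depends on the extraction date, which the protocol itself treats as doubtful.
- *That the spurious odds ratio could reach about 1.4.* That would need reference use to fall linearly to zero. Section 9.5 puts the Danish reference share at about 53% for 2010-2019 and 54% for 2014-2019, which shows no such decline.
- *That the bias exceeds the 2.5 points claimed detectable.* That figure was derived for MC-CLBR per woman, not LBR per cycle, and the illustrated range straddles it.
- *That the HP-hMG comparison is distorted in the same way.* With flat use the loss is equal in both cohorts, and no differential trend is documented there.

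**What to change.** Choose one of two rules and state it in sections 9.1.1 and 9.7.1:

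1. **Move the cut-off.** For Denmark, the last stimulation or frozen-transfer cycle start in Sets 1, 2 and 8 is the last complete DMBR birth date minus 12 months. That is 31 December 2018 if extraction is in August-September 2021. The cut-off in sensitivity analysis 3 then moves back a year, to 31 December 2017.
2. **Move the extraction.** Extract Danish outcomes only once the 2020 DMBR release is available, about the end of January 2022.

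In either case, replace the sentence in section 9.1.1 that waives a Danish restriction because of the IVF register's monthly update; the birth register's lag should govern.

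**Cost of rule 1.** About one year of Danish cycles: 12/120 = 10% of the HP-hMG period and 12/69.2 = 17% of the biosimilar period with even volume, and more of the biosimilar cohort if its use is concentrated late. Section 9.5 expects 75% of 3,000 = 2,250 eligible Danish biosimilar women. If women are lost in the same proportion as cycles, 17.3% fewer leaves about 1,860, just under the 1,900 that Table 3 requires for 2.5 points.

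**Cost of rule 2.** A delay of 4 to 6 months. It affects mainly the Danish interim analysis, which section 6 already calls tentative. Final analysis is not due to start until March 2022. Rule 2 keeps the small Danish biosimilar cohort intact.

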9.4.2 Sweden

The Swedish National Quality Registry of Assisted Reproduction (Q-IVF) is maintained by a regional health authority, the Region Västra Götaland, and has data since 2007. The Q-IVF covers virtually 100% of IVF treatments in the Swedish population (10.4 million in 2020). It contains information on all IVF and IUI records from all IVF clinics in Sweden (currently, 6 public and 13 private). The information in the register includes a range of patient characteristics, all IVF and insemination treatments and their results (including pregnancy outcome). Approximately 20,000 IVF treatments per year are included in the register. Between 1982 and 2006, data was directly reported to the National Board of Health and Welfare with only clustered data (*i.e.*, without personal identification numbers). The Q-IVF used to be updated on a yearly basis, with data on IVF treatments and treatment outcomes becoming available approximately 2 years after the treatment was performed. Starting from 2020, all participating clinics report data on a regular, more frequent basis (33). Data availability lag time may therefore be reduced. Access to the register data for scientific research is applied from the regional health authority, after a dialogue with the authority. Applications are reviewed by a steering committee of the register.

The Swedish Medical Birth Register (SMBR) is managed by the National Board of Health and Welfare and has data since 1973. The register covers 100% of pregnancies when the child is born (live or stillbirth) after the gestational age of at least 22 weeks since July 2008 (week 28 before July 2008). Thus, no data on elective terminations or spontaneous abortions are available and information on stillbirths is only available from the gestational week 22 onwards (week 28 before July 2008). The register contains information reported by reproductive care, covering the duration of pregnancy and the infant period. The information recorded includes data on the mother (e.g. maternal diagnoses and exposures during pregnancy, including drug use since 1995), the delivery and the neonatal care. The data for the previous calendar year is usually available in December. Access to the register data for scientific research is applied from the National Board of Health and Welfare through a standard application procedure.

The Swedish National Patient Register (SNPR) is managed by the National Board of Health and Welfare. The register covers virtually 100% of the Swedish population (10.4 million in 2020). This register includes all inpatient care since 1987 (ICD-10 from 1998) and specialized outpatient care

from 2001 onwards. It does not cover primary care. The register contains information on, e.g., date of admission and discharge, medical department where the patient was treated, patient demographics, diagnoses and procedures. Diagnoses are coded to ICD-10. Procedures are based on the Nordic Classification of Surgical Procedures (NCSP) and the Nordic Classification of Medical Procedures (NCMP). The register is updated annually with a ca 7-9-month lag-time to data access. The register has increased the reporting frequency from healthcare unites to only monthly, and thus more frequent than annual updates of the register for research purposes and faster data access can be expected in the future. Access to the register data for scientific research is decided by the National Board of Health and Welfare through a standard application procedure and is assessed on a case-by-case basis.

The Swedish Prescribed Drug Register (SPDR) is managed by the National Board of Health and Welfare. It covers virtually 100% of the Swedish population (10.4 million in 2020) and contains data on all drugs prescribed to patients in both primary and secondary care. The register has data since July 2005 and is updated monthly. It contains information on all prescribed medicines dispensed by community pharmacies, e.g., date of prescribing and dispensing, brand name, ATC code, strength and package size of the drug, number of packages and DDDs dispensed, and speciality of the prescriber. The prescribed dose and/or the indication, however, are only available as an optional free-text instruction to the patient. Drugs provided at hospitals or medical clinics (i.e., in the inpatient hospital setting) are not included. The data for a specific month is available with ca 14-day lag-time. Access to the register data for scientific research is applied from the National Board of Health and Welfare through a standard application procedure and is assessed on a case-by-case basis.

The Swedish Cause of Death Register is managed by the National Board of Health and Welfare. This register contains data from 1961 and is updated annually. There is also a historical register of causes of death for the years 1952–1960. The register includes all deaths that have occurred in Sweden. This also includes the death of the person was not registered in Sweden at the time of the death. Key variables include age, sex, ethnicity (country of birth and residency), date of death, cause of death (ICD-9/10 codes have been used since 1988), and intent (in cases of injury or poisoning), medical procedures (if death occurred within 4 months after surgery) and autopsy. Stillbirths are not included in the register. The register is updated annually with a ca 6-9-month lag-time to data access for the cause of death variables, however dates of death are available in the register earlier than that.

